Study of the Clinical Efficacy and Safety of Finerenone for the Treatment of IGA Nephropathy

NCT number: KY-2024-081

2023-6-1

Background

Primary IgA nephropathy (IgAN) is an immunopathological diagnostic term for a type of glomerulonephritis characterized by the deposition of IgA or IgA-dominant immune complexes in the glomerular tunica albuginea. And in China IgA nephropathy accounts for about 45% of primary glomerular diseases and about 26% of renal biopsies in patients with chronic failure. Among them, about 15-40% of IgA nephropathy patients progress to renal failure after 10-20 years; IgA nephropathy has become one of the main causes of end-stage renal failure. Therefore, active and effective treatment of IgA nephropathy and delaying the progression of the disease will play a positive role in improving the prognosis of patients, enhancing their quality of life, saving medical resources and reducing the burden of the society and families. For patients with end-stage renal disease, renal replacement therapy has a limited role. Since the pathogenesis of IgA nephropathy is still unclear, there is no sure and effective treatment option until now. Until now, the prognosis can be improved by early intervention to preserve renal function through non-pharmacological strategies and drugs targeting renal disease. For example, ACEI/ARB, SGLT2 drugs, but according to the current pharmacological regimen, some patients will still progress to renal failure. Therefore, new tools are needed.

The non-steroidal glucocorticoid receptor antagonist (MRA)- finerenone reduces the risk of composite renal outcomes, ESKD or renal death in patients with type 2 diabetes and CKD. This was demonstrated in the FIDELIO-DKD and FIGARO-DKD trials. Therefore, in the 2022 KDIGO guidelines, NSAID MRAs are recommended for use in patients with type 2 diabetic nephropathy with normal serum potassium and albuminuria >30 mg/g. According to the current guideline recommendations, NSAID MRAs have limited indications. Therefore it is necessary to conduct clinical studies to explore the scope of clinical indications for finerenone.

Study design and Methods:

This study was a retrospective, non-interventional, multi-centered, observational study. The study started collecting patients in December 2022 and completed in February 2024. Patients diagnosed with IgA nephropathy of any histology who were treated according to standardized practices according to the KDIGO glomerulonephritis guideline, and who were treated for the first time with finerenone were included. The inclusion criteria were age 18 to 75 years, primary IgAN diagnosed by renal biopsy, receive the highest tolerable dose of RASI inhibitors for at least 3 months, serum potassium <5 mmol/L and protein-to-creatinine ratio (PCR) >0.3 mg/g. The exclusion criteria included secondary IgAN, autosomal dominant polycystic kidney disease or autosomal recessive polycystic kidney disease, lupus nephritis, previous renal transplantation, malignant tumor, active malignancy, heart failure with ejection fraction $<40\%$ and followed up less than 6 months. Patients will also be excluded if they stop taking their medication on their own during the follow-up observation period.

This study was conducted at the Fourth Affiliated Hospital of Zhejiang University School of Medicine, the First Affiliated Hospital of Zhejiang University School of Medicine and Jinhua Municipal Centeral Hospital Medical Group. This study was approved by the Ethics Committees of the Fourth Affiliated Hospital of Zhejiang University School of Medicine.

The primary end point was percentage change in PCR from baseline to 6 months. The

secondary end point contained percentage change in PCR from baseline to 1, 2 and 3 months, frequency of patients with a 30% and 50% decrease in PCR and the level of change in clinical indicators, such as eGFR, serum creatinine, albumin, blood sodium and etc.. The focus of the safety analysis was on serious adverse events, decrease in eGFR of more than 30% and 40% from baseline, and hyperkalemia.

We collected clinical data at months 0, 1, 3, and 6 after the use of the drugs by following up and enquiring about their consultation records. Statistical analysis was performed using SPSS software to analyse and compare the baseline data of the two groups, calculate the changes in UACR, blood potassium, and eGFR in the treatment groups, and compare the differences between the groups. It was considered statistically significant when $p<0.05$.

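### Only RAS inhibitors need 3 months of prior use, so a PCR fall from other treatment started shortly before or with finerenone can be attributed to finerenone

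*Protocol*

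**What the plan says.** All references are to the Protocol.

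- **Design** (Study design and Methods): "This study was a retrospective, non-interventional, multi-centered, observational study".
- **Population**: patients "treated according to standardized practices according to the KDIGO glomerulonephritis guideline, and who were treated for the first time with finerenone". Guideline-based care is required, but no period is given over which it must have been stable.
- **Background drug with a duration**: patients must "receive the highest tolerable dose of RASI inhibitors for at least 3 months". No other drug class has a comparable condition.
- **Exclusions**: the list opens with "The exclusion criteria included secondary IgAN, autosomal dominant polycystic kidney disease or autosomal recessive polycystic kidney disease, lupus nephritis, previous renal transplantation, malignant tumor" and goes on to active malignancy, heart failure with low ejection fraction and short follow-up. A separate sentence excludes patients who stop their medication of their own accord during follow-up. No exclusion concerns other treatment that was recently started or changed by a clinician.
- **Other treatment acknowledged** (Background): "For example, ACEI/ARB, SGLT2 drugs, but according to the current pharmacological regimen, some patients will still progress to renal failure".
- **Primary endpoint**: "The primary end point was percentage change in PCR from baseline to 6 months".
- **Analysis**: to "analyse and compare the baseline data of the two groups, calculate the changes in UACR, blood potassium, and eGFR in the treatment groups", with differences between groups tested at p<0.05. The groups are not defined, and the inclusion text admits only first-time finerenone users.
- **Data**: clinical data at months 0, 1, 3 and 6 from follow-up and consultation records, with no list of treatment variables.

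**The concern.** The 3-month RAS-inhibitor condition has a useful effect on the estimate: a drug that has been in place for some time should already be reflected in the baseline PCR, so its effect is not counted again in the change to month 6. That protection covers one class only. If a clinician starts finerenone and an SGLT2 inhibitor at the same visit, or starts a corticosteroid a few weeks earlier, all or part of the second drug's effect falls between month 0 and month 6. A before-after change cannot separate the two.

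The primary endpoint is affected directly, and so are the counts of patients with a 30% or 50% fall in PCR. A patient whose other treatment alone lowers PCR by 30% counts as a 30% responder with no finerenone effect at all. What is at stake is whether the 6-month result can be read as an effect of finerenone, or only as the course of patients who received finerenone along with whatever else was changed.

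**Working it through.** The Protocol gives no effect size, standard deviation, sample size or rate of treatment change, so there is no stated figure to reproduce. The check has two parts.

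**1. Is there any protection apart from the RAS-inhibitor condition?**

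| Element | Does it control other treatment started near month 0? |
|---|---|
| Guideline-standard care | No. It describes the kind of care, not how long it has been stable. |
| RAS inhibitor for at least 3 months | For that class only. |
| Exclusion of patients who stop medication themselves | Not for starts or clinician-directed changes. It may cover self-stopped background drugs, because the medication is not specified. |
| Comparison of two groups | Not as written. The groups are undefined and every included patient takes finerenone. |
| Data at months 0, 1, 3 and 6 | Possibly, if treatment dates are among the clinical data. This is not stated. |

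**2. How large could the effect be if finerenone did nothing?**

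Inputs, all assumed because the documents give none:

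- f = share of patients who start another PCR-lowering drug near month 0;
- g = fractional fall in PCR that this drug causes after the baseline measurement.

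Other patients are taken to have no change.

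- Mean percentage change, the scale closest to the stated endpoint: -f × g.
- Geometric-mean change, if PCR is analysed on the log scale: (1 - g)^f - 1.

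| f | g | Mean percentage change | Geometric-mean change |
|---|---|---|---|
| 20% | 30% | -0.2 × 0.3 = -6% | 0.7^0.2 - 1 = -6.9% |
| 30% | 40% | -0.3 × 0.4 = -12% | 0.6^0.3 - 1 = -14.2% |
| 40% | 50% | -0.4 × 0.5 = -20% | 0.5^0.4 - 1 = -24.2% |

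On the 30% responder endpoint, every patient in the first row who starts such a drug reaches the threshold, so up to 20% of the cohort could be responders for this reason alone.

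**Opposite direction.** Stopping a drug that had lowered PCR by g raises PCR by 1/(1 - g) - 1. With g = 30% this is 1/0.7 - 1 = +42.9%. If 20% of patients start such a drug and another 10% stop one, the mean change is -6% + 0.1 × 42.9% = -1.7%. The net bias therefore depends on the balance of starts and stops, which only treatment dates can show.

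**The case against.** The strongest reply has four parts.

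**This belongs in the SAP.** Covariate adjustment and sensitivity analyses are commonly left to an SAP, and none is shown here. That stands: their absence from the Protocol is not in itself a fault. But which patients enter and which treatment dates are extracted are protocol matters, and an SAP cannot adjust for dates that were never collected.

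**Treatment data may have been collected.** This also stands. The clinical data are not itemised, and the planned baseline comparison could include background drugs. A reader might infer that co-treatment was not recorded; the text supports only that recording is not stated.

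**Nobody is shown to have changed treatment.** Correct. A reader might conclude that the PCR fall will be wrongly credited to finerenone, or that the bias must favour it. The documents support neither: they give no rate of treatment changes, a drug started well before month 0 is already partly in the baseline, and stops push the other way. Corticosteroids and immunosuppressants are not named in the Protocol at all. They are included here because the eligibility text does not limit them.

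**There is a comparison of two groups.** A defined concurrent comparator could reduce the problem, but only if co-treatment were recorded and either balanced or adjusted for. No such group is described. The undefined groups are the wider defect, and unstable co-treatment is one route by which it biases the result.

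The upper range in the table might also suggest that the bias could equal a full finerenone effect. The Protocol gives no expected effect, so that comparison cannot be made.

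**Conclusion.** The point holds in a conditional form. The Protocol applies a stability safeguard to RAS inhibitors and to no other PCR-lowering treatment, although its own Background names a second relevant class. Under the eligibility and analysis as written, an effect of other treatment started shortly before or with finerenone cannot be told apart from an effect of finerenone.

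The table shows what could happen and does not estimate what did. It rests on assumed f and g, no finerenone effect, and starts only. The figures nearest the stated endpoint are those on the arithmetic percentage-change scale; the geometric figures apply only if a log-scale analysis is used.

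This should be corrected because it bears on the interpretation of the primary result and the remedy is inexpensive. It does not show that the result is wrong.

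**What to change.** 1. **Extract dates.** From 3 months before the first finerenone dose to month 6, record start, stop and dose-change dates of SGLT2 inhibitors, corticosteroids, other immunosuppressants and RAS inhibitors.
2. **Keep the full-cohort analysis** of the 6-month PCR change.
3. **Pre-specify one sensitivity analysis** of the same endpoint in patients whose background treatment was unchanged in the 3 months before and at month 0. Report it beside the full-cohort result, and limit any claim of a finerenone effect to what both support.
4. **Handle changes after month 0 separately.** Describe them, or add a further analysis such as one using PCR values obtained before the change. Do not make stability through month 6 the main restriction: treatment is more likely to be intensified in patients whose PCR has not fallen, so excluding them can inflate the apparent benefit.
5. **If two groups are compared**, define them and include baseline background treatment as a covariate.

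The cost is extra extraction from the consultation records already in use and one added analysis. The stable-background subset will be smaller and its interval wider. It remains uncontrolled, so agreement between the two results removes this one explanation in part and does not establish a causal effect. No patient leaves the main analysis and no care is altered.

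### The new-user rule covers finerenone but no other mineralocorticoid receptor antagonist (MRA), so a patient already on another MRA at month 0 is eligible and the baseline need not be MRA-free

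*Protocol*

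**What the plan says.** All of the relevant text is in the protocol.

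- **Exposure rule** (Study design and Methods): the cohort consists of patients "who were treated for the first time with finerenone were included". New use is defined for this one drug.
- **Other treatment and laboratory conditions** (same section): guideline-based care, and patients must "receive the highest tolerable dose of RASI inhibitors for at least 3 months, serum potassium <5 mmol/L". A PCR threshold also applies.
- **Exclusions** (same section): the list opens "The exclusion criteria included secondary IgAN, autosomal dominant polycystic kidney disease or autosomal recessive polycystic kidney disease, lupus nephritis, previous renal transplantation" and goes on to malignancy, heart failure with a low ejection fraction, short follow-up, and patients who stop their medication on their own. It does not mention another MRA.
- **Outcomes** (same section): "The primary end point was percentage change in PCR from baseline to 6 months". The secondary endpoints include the share of patients whose PCR falls by 30% and by 50%. The safety focus includes "decrease in eGFR of more than 30% and 40% from baseline, and hyperkalemia".
- **Drug class** (Background): "The non-steroidal glucocorticoid receptor antagonist (MRA)- finerenone". The name is expanded wrongly, but the abbreviation places finerenone among the MRAs.

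**The concern.** The primary endpoint is a change from month 0, so its meaning depends on what treatment the patient was on at month 0. The protocol recognises this for RAS inhibitors: it requires a settled background of at least 3 months before finerenone starts. It sets no corresponding condition for finerenone's own class.

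A patient who took another MRA until the day finerenone began is a first-time finerenone user. For that patient the 6-month change compares one MRA with another. If the earlier drug was continued, it measures finerenone on top of an MRA. Neither is the effect of adding finerenone to RAS inhibition, which is what the Background's aim of exploring new indications needs. The responder rates and the hyperkalaemia results would be affected by the same mixture.

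Who enters the cohort is an eligibility matter and is fixed in the protocol, so the gap is not one that a protocol would ordinarily leave to the SAP.

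**Working it through.** The protocol gives no sample size, effect size or switcher share, so there is no figure of its own to reproduce. The check has two parts.

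**1. Eligibility, read criterion by criterion.** Take a patient with biopsy-proven primary IgAN, within the age range, on the required RAS-inhibitor background, and taking another MRA up to month 0.

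- First use of finerenone: met.
- RAS-inhibitor condition, "receive the highest tolerable dose of RASI inhibitors for at least 3 months": met; it says nothing about MRAs.
- Potassium and PCR limits, "serum potassium <5 mmol/L and protein-to-creatinine ratio (PCR) >0.3 mg/g": these can be met while on an MRA.
- Exclusions: none applies on account of the earlier drug.

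The patient is eligible under every stated criterion.

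**2. Size, for illustration only.** Every input here is an assumption. Let s be the share of switchers.

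*PCR, geometric-mean scale.* Assume a 30% fall in MRA-naive patients and no change in switchers. The observed fall is 1 − exp[(1 − s) × ln 0.70] = 1 − 0.70^(1 − s).

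| s | Calculation | Observed fall | Shift from 30% |
|---|---|---|---|
| 10% | 1 − 0.70^0.9 | 27.5% | 2.5 points |
| 20% | 1 − 0.70^0.8 | 24.8% | 5.2 points |
| 30% | 1 − 0.70^0.7 | 22.1% | 7.9 points |

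*PCR, arithmetic-mean scale.* The observed change is (1 − s) × naive change + s × switcher change.

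- Naive −30%, switchers 0%: −27.0%, −24.0% and −21.0% at s = 10%, 20% and 30%.
- Naive −30%, switchers −15%: −28.5%, −27.0% and −25.5%.
- Naive −20% to −40%, switchers from zero to half the naive effect: the shift is s × (switcher change − naive change). At s = 10% it runs from 0.1 × 10 = 1 point to 0.1 × 40 = 4 points. At s = 30% it runs from 0.3 × 10 = 3 points to 0.3 × 40 = 12 points.

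*Hyperkalaemia.* Assume 10% in naive patients and s = 30%.

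- Switchers 2%: 0.7 × 10 + 0.3 × 2 = 7.6%.
- Switchers 5%: 0.7 × 10 + 0.3 × 5 = 8.5%.
- Switchers 15%: 0.7 × 10 + 0.3 × 15 = 11.5%.

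The sign therefore depends on which kind of switcher is present. At s = 0 there is no distortion of any outcome.

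**The case against.** The strongest reply is that this is a possibility and not a demonstrated fault. The protocol mentions no switch and no MRA-treated patient; the drug examples in the Background are ACEI/ARB and SGLT2 drugs. It also does not say that other MRAs move PCR or potassium as finerenone does. That is an assumption drawn from the shared class. This objection stands as far as it goes. A reader might infer that the results are distorted, and the documents do not support that, because no switcher is shown to be in the cohort.

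A reader might also infer that first finerenone use is the only entry condition. It is not. The RAS-inhibitor, potassium and PCR conditions apply too, although none of them removes an MRA user.

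A third tempting inference is that switchers lower the hyperkalaemia rate because those who developed it on an earlier MRA are absent. No criterion excludes such patients. The potassium limit may favour those who tolerated an MRA. But someone whose potassium recovered after stopping an earlier MRA can enter, and concurrent use of both drugs could raise the rate. The direction is open.

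On efficacy, dilution is the plausible direction but not a certain one: a patient who stopped the other drug well before month 0 may have an off-drug baseline. If dilution occurs, it understates benefit and does not create it. The modelled shifts are modest at small shares, and the protocol states no decision threshold that they would cross.

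Finally, reporting switchers separately could be left to a SAP. That is fair for the reporting, but not for the entry rule, which the protocol has fixed too loosely. The planned comparison between two groups is no remedy either: the protocol does not define the groups, and no criterion balances earlier MRA use between them.

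**Conclusion.** The point holds in a limited form. The new-user rule covers finerenone alone, and a patient on another MRA up to month 0 meets every criterion as written. If such patients are in the cohort, their baseline PCR and potassium may already reflect MRA treatment, and the pooled 6-month change cannot be read as the effect of adding finerenone to RAS inhibition. The PCR fall and responder rates would most plausibly be understated, and the hyperkalaemia rate could move in either direction.

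The size is unknown, because the documents give neither the share of switchers nor their response. The calculations above only set a scale: a few points at a 10% share, and up to 12 points at 30% under the most extreme inputs tried. This is worth correcting because it bears on the interpretation of the primary endpoint and the correction is cheap. It is not evidence that the result is wrong.

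**What to change.** - Extract use of any other MRA from the records over a fixed look-back before month 0, for example the same 3 months as the RAS-inhibitor rule, and note whether it continued after finerenone began.
- Make patients with no other MRA in that window the primary analysis set.
- Report PCR change, responder rates and hyperkalaemia with and without the remaining patients, and state how many there are. If there are none, one sentence saying so closes the matter.

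The work is small. The study already draws on consultation records, and checking the RAS-inhibitor rule already needs a 3-month treatment history; that the same records list other MRAs is an assumption to confirm.

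The cost is precision. With an unchanged standard deviation, removing a share s multiplies the standard error by 1/√(1 − s): 1/√0.9 = 1.05, 1/√0.8 = 1.12 and 1/√0.7 = 1.20 at 10%, 20% and 30%. The loss is therefore slight if switchers are few, and larger in just the case where they would matter most.

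A 3-month window would still admit a patient who stopped another MRA earlier than that, for instance because of hyperkalaemia. The report should state this limit, or a longer look-back should be used where the records allow.

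### The proteinuria entry limit, PCR >0.3 mg/g, is implausibly low and probably a unit slip; read literally, it puts no meaningful floor under the denominator of the primary end point

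*Protocol*

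**What the plan says.** The inclusion criteria are in the Protocol, under Study design and Methods. The proteinuria criterion appears once, together with potassium: "serum potassium <5 mmol/L and protein-to-creatinine ratio (PCR) >0.3 mg/g". No second unit, conversion or other proteinuria limit is given.

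The other entry conditions set no numeric floor on proteinuria. The population is described as "Patients diagnosed with IgA nephropathy of any histology who were treated according to standardized practices", and the criteria begin "The inclusion criteria were age 18 to 75 years, primary IgAN diagnosed by renal biopsy". What remains is prior RAS inhibitor treatment, the potassium limit, management in line with the KDIGO guideline, and first use of finerenone.

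The end points are relative to baseline PCR: "The primary end point was percentage change in PCR from baseline to 6 months", and among the secondary ones, "frequency of patients with a 30% and 50% decrease in PCR".

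The only other urinary threshold in the document is in the Background, where a guideline recommendation for type 2 diabetic nephropathy is described for patients "with normal serum potassium and albuminuria >30 mg/g".

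**The concern.** The value is a valid ratio, but it is far too small to work as a proteinuria criterion. A limit that almost every patient passes selects nobody, yet it is listed as a selection rule.

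A wrong label does not by itself change a percentage: PCR at 6 months divided by PCR at baseline is the same number in any unit. The risk comes through selection. If records were screened on the literal value, patients with very low baseline PCR were eligible, and in them a small absolute fluctuation gives a large relative change. A percentage fall cannot exceed 100%, whereas a percentage rise has no upper limit, so low baselines mainly stretch the upper tail of the primary end point. The absolute fall needed to count as a 30% or 50% responder also shrinks with baseline.

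Even if nobody screened on the literal value, a reader cannot tell from the document which patients were eligible, and the three participating hospitals could have read the criterion differently.

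**Working it through.** The document gives no calculation behind this limit, so there is no figure of its own to reproduce. The check is unit conversion followed by percentage arithmetic.

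**Inputs**
- Written limit: PCR 0.3 mg/g (Protocol, inclusion criteria).
- Assumed intended limit: 0.3 g/g. The document does not state it. A reading of 0.3 mg/mg gives the same value.
- Albuminuria level: 30 mg/g (Protocol, Background). It concerns another analyte and another disease, so it serves only as a check on order of magnitude.
- Conversion: 1 g/g = 1 mg/mg = 1000 mg/g.

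**Step 1: size of the discrepancy**
- Written limit: 0.3 / 1000 = 0.0003 g/g.
- Assumed intended limit: 0.3 × 1000 = 300 mg/g.
- Ratio: 300 / 0.3 = 1000.
- Against the Background figure: 30 / 0.3 = 100. Albumin is part of total protein, so a total-protein limit 100 times below an albumin level is not credible as a proteinuria criterion.

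**Step 2: what the limit means per day**

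Daily protein = PCR × daily creatinine excretion, here assumed to be 0.5 to 2 g/day.
- At 0.3 mg/g: 0.3 × 0.5 = 0.15 mg/day to 0.3 × 2 = 0.6 mg/day.
- At 300 mg/g: 300 × 0.5 = 150 mg/day to 300 × 2 = 600 mg/day.

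**Step 3: effect of baseline on the end points**

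Percentage change = 100 × absolute change / baseline. The absolute changes below are assumed, for illustration.

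| Baseline PCR (mg/g) | Change +10 mg/g | Change +30 mg/g | Change +50 mg/g | Fall needed for 30% response | Fall needed for 50% response |
|---|---|---|---|---|---|
| 300 | +3.3% | +10% | +16.7% | 0.30 × 300 = 90 mg/g | 0.50 × 300 = 150 mg/g |
| 30 | +33.3% | +100% | +166.7% | 0.30 × 30 = 9 mg/g | 0.50 × 30 = 15 mg/g |
| 0.3 | +3333% | +10,000% | +16,667% | 0.30 × 0.3 = 0.09 mg/g | 0.50 × 0.3 = 0.15 mg/g |

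The last row is the arithmetic extreme of the written rule, not an expected patient. The row at 30 mg/g is more informative: it lies well inside the literal limit, and the same absolute change counts ten times as much there as at 300 mg/g.

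**Step 4: what cannot be computed**

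The document gives neither the baseline PCR distribution nor the limit actually applied. The number of patients between 0.3 and 300 mg/g, and any effect on the results, therefore cannot be estimated.

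**The case against.** The strongest reply is that the harm is conditional and its condition is unlikely. If this is a slip of the pen, the investigators had a sensible value in mind and probably screened on it; the defect is then confined to the text. The cohort is also selected in other ways: biopsy-proven disease, at least 3 months of maximally tolerated RAS inhibition, guideline-based care, and a decision to start finerenone. Such patients probably had PCR well above 0.3 mg/g. The 1000-fold figure rests on an assumed 300 mg/g, and the 30 mg/g comparison crosses analytes and diseases. The text was also read by machine, so a lost character cannot be excluded, although nothing points to one.

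Much of this stands, and it limits the weight of the point. No distortion of results is shown, the direction and size of any bias in the response frequencies are unknown, and the intended value is for the sponsor to state.

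It does not remove the defect. The written rule is an eligibility threshold, not background prose, and it is stated only once. The other entry conditions, as the document words them, set no proteinuria floor. That they probably kept very low values out is a guess about the cohort, and the records can settle it.

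**Conclusion.** The concern holds. As written, the PCR criterion cannot function as a proteinuria limit, and it leaves the denominator of the primary end point and of the 30% and 50% response end points without a meaningful lower bound. If 0.3 g/g was intended, the written limit is too low by a factor of 1000; that factor depends on the assumption. That the value is implausibly low does not depend on it.

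The consequence has two branches. If the intended limit was applied, only the written criterion is wrong. If the literal limit was applied, patients below the intended limit were eligible, in a number the document does not reveal. Confidence is high for the defect in the text; no claim is made about the results. It should be fixed, because it governs who contributes to the primary end point and is cheap to settle.

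**What to change.** 1. The sponsor confirms the intended number and unit of the PCR limit (300 mg/g is only an assumption here) and corrects the criterion.
2. The sponsor states the threshold actually used to select records, and confirms that all three hospitals used the same one.
3. The baseline PCR of the extracted records is checked against the confirmed limit. The protocol says "The study started collecting patients in December 2022 and completed in February 2024", so this is a matter of record.
4. Only if the check shows that the literal value was used is the cohort re-screened against the confirmed limit.

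The cost is a text correction and a record check. Re-screening, if needed, may remove some patients with low proteinuria; how many cannot be estimated from the document.

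### Two exclusion rules depend on what happens after finerenone starts, so safety rates and PCR change come from a cohort selected on post-baseline events

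*Protocol*

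**What the plan says.** All the relevant text is in the Protocol, Study design and Methods.

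- **Entry:** the cohort consists of patients "who were treated for the first time with finerenone were included", so time zero is first use.
- **Follow-up rule:** the list of exclusions ends with patients "and followed up less than 6 months".
- **Stopping rule:** "Patients will also be excluded if they stop taking their medication on their own during the follow-up observation period".
- **Schedule:** "We collected clinical data at months 0, 1, 3, and 6 after the use of the drugs".
- **Primary efficacy measure:** "The primary end point was percentage change in PCR from baseline to 6 months".
- **Earlier efficacy measures, listed among other items:** "secondary end point contained percentage change in PCR from baseline to 1, 2 and 3 months".
- **Safety:** "The focus of the safety analysis was on serious adverse events, decrease in eGFR of more than 30% and 40% from baseline, and hyperkalemia".
- **Comparison:** the analysis is to "compare the baseline data of the two groups" and compare differences between groups.

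The section describes no population of all starters and no separate safety population.

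**The concern.** A cohort that starts at first use should be defined by what is known at first use. Here two conditions look forward from that point. The retrospective design does not change this: the facts are known when records are selected, but they arise after treatment has begun.

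For safety, a patient who has a serious adverse event, an eGFR fall or hyperkalemia and then stops without medical direction, or is lost before month 6, leaves both numerator and denominator. If the 6 months run from first use and a death counts as short follow-up, no death before month 6 can be counted. The text settles neither point.

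For efficacy, the 6-month rule acts on the primary end point much like a complete-case rule. It goes further for the month 1 to 3 secondary end points. These do not need 6 months of follow-up, yet patients with observed values at those times are removed.

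The study sets out to describe the efficacy and safety of finerenone. The results will instead describe patients who did not stop by their own decision and stayed under observation.

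**Working it through.** **Step 1: when each rule can be judged.** The stopping rule is tied expressly to the follow-up period, so it is post-baseline on its face. The follow-up rule names no starting point. The only follow-up the section describes is data collection at months 0, 1, 3 and 6 after drug start, so the natural reading is 6 months from first use, which is also post-baseline.

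**Step 2: inputs.** The Protocol states no event rate, stop rate, dropout rate or expected PCR change, so there is no figure of its own to reproduce. Every input below is an assumption, chosen to show the range in both directions.

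**Step 3: safety.** Let p be the true risk in all starters, and q and r the shares of affected and unaffected patients who are excluded.

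Reported risk = p(1 − q) / [p(1 − q) + (1 − p)(1 − r)]

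Example with p = 0.10, r = 0.20, q = 0.50: 0.10 × 0.50 / (0.10 × 0.50 + 0.90 × 0.80) = 0.05 / 0.77 = 6.5%.

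Reported risk with r = 0.20:

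| True risk | q = 10% | q = 20% | q = 25% | q = 50% | q = 75% |
|---|---|---|---|---|---|
| 5% | 5.6% | 5.0% | 4.7% | 3.2% | 1.6% |
| 10% | 11.1% | 10.0% | 9.4% | 6.5% | 3.4% |
| 15% | 16.6% | 15.0% | 14.2% | 9.9% | 5.2% |

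The reported risk is too low exactly when q > r and too high when q < r. At p = 10% the total share excluded runs only from 19.0% to 25.5% across the row, so the overall number excluded reveals little about the bias.

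**Step 4: loss unrelated to outcome.** If a further share a of patients is removed whatever their outcome, both terms of the denominator and the numerator are multiplied by (1 − a), and the factor cancels. Purely administrative short follow-up therefore need not bias.

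**Step 5: PCR.** Assume a 35% geometric-mean fall in retained patients (ratio to baseline 0.65), a fraction d excluded, and a ratio g in those excluded.

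All-starters change = exp[(1 − d) ln 0.65 + d ln g] − 1

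Example with d = 0.30, g = 1.0: exp(0.70 × ln 0.65) − 1 = −26.0%.

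| Change in excluded patients | d = 10% | d = 20% | d = 30% |
|---|---|---|---|
| −50% (g = 0.5) | −36.7% | −38.3% | −39.9% |
| −35% (g = 0.65) | −35.0% | −35.0% | −35.0% |
| −20% (g = 0.8) | −33.6% | −32.2% | −30.8% |
| none (g = 1.0) | −32.1% | −29.2% | −26.0% |
| +20% (g = 1.2) | −30.9% | −26.5% | −21.9% |

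The reported fall overstates the effect if excluded patients responded less and understates it if they responded more. No size is claimed for a comparison between the two groups, where even the direction depends on how exclusion differs by group.

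**The case against.** The strongest case on the other side has four parts.

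1. **The stopping rule is narrow.** It covers only patients who stop by their own decision. Hyperkalemia and eGFR decline are laboratory findings, and a stop ordered by a clinician in response is not caught if 6 months of follow-up exist. The medication concerned is not even named as finerenone. This stands, and it makes the heavier exclusion scenarios (50% to 75% of affected patients) possible rather than supported by the document.
2. **Much short follow-up may be calendar-driven.** Collection ran from December 2022 to February 2024. If February 2024 was also the data cut-off, which the text does not say, anyone starting after about August 2023 fails the 6-month rule for date reasons alone. Such loss cancels, as shown above. This also stands, but the rule as written does not separate it from death, adverse events or loss to follow-up.
3. **The figures rest on assumptions and run both ways.** True. They show how sensitive the results are and do not estimate the bias.
4. **Analysis sets and reporting of exclusions often sit in a SAP, which is not at hand.** A SAP or report could indeed give numbers and reasons. But these are eligibility rules fixed in the Protocol, and analysis sets are normally drawn from the patients those rules admit.

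These points limit the extent of the problem. None removes the selection.

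**Conclusion.** The concern holds and should be fixed. The stopping rule is post-baseline by its wording, and the follow-up rule is so on the natural reading that the 6 months start at first use. Nothing in the Protocol offsets either rule.

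That the cohort is selected on later events is certain. The size and direction of any bias are not: they depend on how often, and why, patients were removed, and the document gives neither. Data from the retained patients alone cannot supply this.

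**What to change.** - **Cohort:** define it by criteria known at first finerenone use and delete both post-baseline exclusions. If the 6-month rule is meant as an administrative cut-off, restate it as first use at least 6 months before the data cut-off.
- **Safety:** count events in all patients with at least one dose, from first dose to last contact, and report follow-up time.
- **PCR:** analyse all starters with a baseline value, using every recorded post-baseline value. Add a sensitivity analysis that varies the missing month-6 change in both directions, for example −50%, 0% and +20%.
- **Reporting:** give numbers and reasons for stopping and for short follow-up (administrative, death, adverse event, improvement, lost), by group if two groups are compared.
- **Current cohort:** keep the adherent completers as a labelled sensitivity analysis.

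The cost is protocol wording and extra record extraction for the patients now dropped, with no new procedures. The document does not say whether their records were kept. Where they were not, at least the numbers and known reasons should be reported. Month-6 PCR will then have missing values that need an explicit assumption, and the headline figures may shift, possibly to less favourable ones.
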